6.3.4. Investigator Evaluation of Adverse Events

The investigator will evaluate all adverse events with respect to seriousness (criteria for serious are listed in Section 6.3.2.2), severity (intensity) and causality (relationship to belimumab). The investigator will make an assessment of intensity for each AE and SAE based on the Division of Microbiology and Infectious Diseases (DMID), 2001 Adverse Event Severity Grade Tables (see Appendix 6), where possible:

SEVERITY:

Mild - An event that is easily tolerated by the subject, causing minimal discomfort and not interfering with everyday activities (Grade 1 DMID)

Moderate - An event that is sufficiently discomforting to interfere with normal everyday activities (Grade 2 DMID)

Severe - An event that prevents normal everyday activities (Grade 3 or 4 DMID)

An AE that is assessed as severe will not be confused with an SAE. Severity is a category utilized for rating the intensity of an event; and both AEs and SAEs can be assessed as severe. An event is defined as 'serious' when it meets at least one of the pre-defined outcomes as described in the definition of an SAE.

6.3.5. Pregnancy

Any pregnancy that occurs during study participation and through 16 weeks following the last dose must be reported using a clinical trial pregnancy form. To ensure subject safety, each pregnancy must be reported to GSK within 2 weeks of learning of its occurrence. The pregnancy must be followed up to determine outcome (including premature

termination) and status of mother and child. Pregnancy complications and elective terminations for medical reasons must be reported as an AE or SAE. Spontaneous abortions must be reported as an SAE.

Any SAE occurring in association with a pregnancy brought to the investigator's attention after the subject has completed the study and considered by the investigator as possibly related to the study treatment, must be promptly reported to GSK.

In the event that a subject becomes pregnant during the study, they should discontinue the study medication and be withdrawn from the study.

6.3.6. Time Period and Frequency of Detecting AEs and SAEs

The investigator or site staff is responsible for detecting, documenting and reporting events that meet the definition of an AE or SAE.

AEs will be collected from the start of study treatment (Week 0) and until the 16 week follow up visit.

SAEs will be collected over the same time period as stated above for AEs. However, any SAEs assessed **as related** to study participation (e.g., study treatment, protocol-mandated procedures, invasive tests, or change in existing therapy) or related to a GSK concomitant medication, will be recorded from the time a subject consents to participate in the study up to and including any follow up contact. All SAEs will be reported to GSK within 24 hours, as indicated in Section [6.3.7](#).

6.3.7. Prompt Reporting of Serious Adverse Events and Other Events to GSK

SAEs, pregnancies and liver function abnormalities meeting pre-defined criteria will be reported promptly by the investigator to GSK as described in the following table once the investigator determines that the event meets the protocol definition for that event.

Type of Event	Initial Reports		Follow-up Information on a Previous Report	
	Time Frame	Documents	Time Frame	Documents
All SAEs	24 hours	"SAE" data collection tool	24 hours	Updated "SAE" data collection tool
Pregnancy	2 Weeks	Pregnancy Notification Form	2 Weeks	Pregnancy Follow up Form
Liver chemistry abnormalities Phase III-IV:				
ALT \geq 3xULN and Bilirubin \geq 2xULN (>35% direct) (or ALT \geq 3xULN and INR>1.5, if INR measured)***	24 hours*	SAE data collection tool. **Liver Event CRF and liver imaging and/or biopsy CRFs if applicable	24 hours	Updated SAE data collection tool. **Updated Liver Event CRF
ALT \geq 8xULN; ALT \geq 5xULN with hepatitis or rash or \geq 3xULN and <5xULN that persists \geq 4 weeks	24 hours*	**Liver event CRF	24 hours	**Updated Liver Event CRF
ALT \geq 5xULN plus bilirubin <2xULN	24 hours*	**Liver event CRF does not need completing unless elevations persist for 2 weeks or subject cannot be monitored weekly for 2 weeks	24 hours	
ALT \geq 5xULN and bilirubin <2xULN that persists \geq 2 weeks	24 hours*	**Liver event CRF	24 hours	Updated liver event CRF
ALT \geq 3xULN and <5x ULN and bilirubin <2xULN	24 hours*	**Liver event CRF does not need completing unless elevations persist for 4 weeks or subject cannot be monitored weekly for 4 weeks		

*GSK to be notified at onset of liver chemistry elevations to discuss subject safety.

** Liver event documents should be completed as soon as possible.

*** INR measurement is not required; if measured, the threshold value stated will not apply to patients receiving anticoagulants

Criteria for liver chemistry stopping and follow up criteria can be found in Section 6.3.1.

The method of detecting, recording, evaluating and follow-up of AEs and SAEs plus procedures for completing and transmitting SAE reports to GSK are provided in the SPM. Procedures for post-study AEs/SAEs are provided in the SPM.

6.3.7.1. Regulatory Reporting Requirements for SAEs

Prompt notification of SAEs by the investigator to GSK is essential so that legal obligations and ethical responsibilities towards the safety of subjects are met.

GSK has a legal responsibility to notify both the local regulatory authority and other regulatory agencies about the safety of a product under clinical investigation. GSK will comply with country specific regulatory requirements relating to safety reporting to the regulatory authority, Institutional Review Board (IRB)/Independent Ethics Committee (IEC) and investigators.

Investigator safety reports are prepared for suspected unexpected serious adverse reactions according to local regulatory requirements and GSK policy and are forwarded to investigators as necessary.

An investigator who receives an investigator safety report describing a SAE(s) or other specific safety information (e.g., summary or listing of SAEs) from GSK will file it with the IB and will notify the IRB/IEC, if appropriate according to local requirements.

6.3.7.2. Disease-Related Events and/or Disease-Related Outcomes Not Qualifying as SAEs

The following conditions (preferred terms; MedDRA v. 14.0) are disease-related events (DRE) that can occur in the study population regardless of belimumab exposure.

When these conditions are considered SAEs, they must be reported to the sponsor within 24 hours of site personnel becoming aware as described in Section 6.3.6. However, because these events are typically associated with the disease under study, the sponsor will not submit these events as expedited reports to regulatory authorities, investigators, or IRBs/IECs (unless considered by the sponsor to be related to study agent).

Butterfly rash	Lupus pancreatitis
Cutaneous lupus erythematosus	Lupus pneumonitis
Glomerulonephritis membranoproliferative	Lupus vasculitis
Glomerulonephritis membranous	Nephritic syndrome
Glomerulonephritis proliferative	Nephritis
Lupus encephalitis	Neuropsychiatric lupus
Lupus endocarditis	Pericarditis lupus
Lupus enteritis	Peritonitis lupus
Lupus hepatitis	SLE arthritis
Lupus myocarditis	Systemic lupus erythematosus rash
Lupus nephritis	Systemic lupus erythematosus

6.3.8. Laboratory Evaluations

Clinical laboratory tests will consist of a complete blood count (CBC) with differential, Chem-20, magnesium, and urinalysis (see list in [Appendix 5](#)). At the discretion of the Investigator, additional samples may be taken for safety reasons. Immunoglobulins, autoantibodies and serum complement (C3 and C4), will also be assessed (see [Section 6.4](#)). Samples (blood and urine) for clinical laboratory tests will be collected as described in the Time and Events schedule ([Table 2](#) and [Table 3](#)).

All clinical laboratory blood samples will be sent to a central laboratory for analysis (details provided in the SPM). Standard reference ranges will be used. Full details of the collection and shipping requirements for the central laboratory are provided in the Central Laboratory Investigator Manual. The central laboratory will fax laboratory results to the Investigator and will transmit the results electronically to GlaxoSmithKline.

6.3.9. Infusion-related Reactions and Hypersensitivity Reactions

Infusion-related reactions on the day of an infusion occurred in approximately 17% of patients treated with belimumab 1mg/kg or 10mg/kg during the double-blind portion of the Phase 2 and 3 SLE studies, but at rates similar to placebo (15%). Most infusion-related/hypersensitivity events have been mild-moderate in nature; however, severe and or serious events have been reported infrequently (<2% of patients). These events have included reports of rash, urticaria, angioedema, hypotension and anaphylaxis. As has been done in recent protocols, this protocol recommends that administering premedication for prophylaxis against infusion reactions and hypersensitivity reactions should be considered for subjects with a history of allergies or urticaria.

In the post-marketing setting, delayed onset of symptoms of acute hypersensitivity reactions has been observed. Subjects should remain under clinical supervision for 3 hours after completion of the first 2 infusions. Should symptoms of acute hypersensitivity occur, an extended period of monitoring may be appropriate, based on clinical judgment. Subjects should be made aware of the potential risk, the signs and symptoms of such reactions, and the importance of immediately seeking medical attention.

6.3.10. Other Immunosuppression Related Considerations

Although there is no evidence to date for an increased risk with belimumab treatment, the possibility of immunosuppression resulting in an increase in the frequency and/or severity of infection and/or an increased risk of malignancy cannot be excluded. During the trial, subjects will be questioned at all study visits about adverse events and results recorded in the eCRF. Examinations and laboratory evaluations will be performed routinely and the results, including markers of potential immunosuppression, will be reported to the investigators.

6.3.10.1. Progressive Multifocal Leukoencephalopathy

Progressive multifocal leukoencephalopathy (PML) resulting in neurological deficits, including fatal cases, has been reported in SLE patients receiving immunosuppressant pharmacotherapy, including belimumab. A diagnosis of PML should be considered in any subject presenting with new-onset or deteriorating neurological signs and symptoms. The subject should be referred to a neurologist or other appropriate specialist for evaluation. If PML is confirmed, study agent should be discontinued and consideration should be given to stopping immunosuppressant therapy.

If PML is suspected, this should be immediately reported to the Medical Monitor.

The appropriateness of continuing study agent, while the case is being assessed, should be discussed.

6.3.11. Vital Signs and Weight

Systolic and diastolic blood pressure (sitting), heart rate, and oral temperature will be measured. Measurements of vital signs and weight will be taken prior to dosing on Day 0 and every 4 weeks up to week 48/Exit; and at the 16-week follow-up visit (vital signs only) for subjects who withdraw prior to study completion. At the discretion of the Investigator, vital signs may be assessed at unscheduled visits.

6.3.12. Physical Examination

Abbreviated, symptom-driven examinations will be performed at Day 0, every 24 weeks, at the study Exit, and at the 16-week follow-up visit for subjects who withdraw. At the discretion of the Investigator, physical examinations may be performed at unscheduled visits.

As a minimum, brief physical examination will include assessment of the skin, lungs, cardiovascular system, and abdomen (liver and spleen).

6.3.13. Immunogenicity

6.3.13.1. Sample Collection and Handling

Serum samples will be collected for belimumab immunogenicity assays prior to dosing at Day 0, and Weeks 24 and 48 of Year 1 and Year 2, etc., and at the Exit visit, and 16 week follow-up visit. An attempt will be made to obtain a serum sample for anti-belimumab antibodies at least 6 months after the last dose of study agent for any subject who had an anti-belimumab antibody response at the 16-week follow-up visit (or last study visit at which immunogenicity was assessed if the 16-week follow-up immunogenicity sample is not available).

At each collection time, blood will be collected in a 6 mL plain tube. Each specimen will be allowed to clot, and the tube then centrifuged at approximately 1,600 g for 15 minutes at room temperature to separate the clot from the serum. The serum (approximately 1 mL per sample) will be harvested and placed in duplicate 2-mL Sarstedt vials for storage. Serum samples will be stored at -20°C at the sites before weekly batch shipment to Quest

Diagnostics. Samples will be stored at -70°C at Quest Diagnostics until shipment to HGS and stored at -80°C after they arrive at HGS. Samples will be shipped on dry ice in both shipments.

6.3.13.2. Assay Methods

Immunogenicity testing will be carried out at GSK (Clinical Immunology department) or Frontage Laboratories in Shanghai, China. The assay is performed in a 4-tiered belimumab immunogenicity assay paradigm (screening, confirmation/specificity and neutralisation and titer).

In the screening assay, the presence of anti-belimumab antibodies will be assessed using an electrochemiluminescence (ECL)-based (Meso Scale Discovery [MSD]) bridging assay after dissociation of belimumab from the anti-drug antibodies (ADA). Any samples testing positive will then be tested using a confirmatory ECL based assay which is able to distinguish between ADA (true positive) and BLyS-belimumab complexes in serum (false positive). The confirmed positive samples will be analyzed for the presence of neutralizing antibodies by a neutralisation assay and also assayed for titer. The results of the anti-belimumab antibody tests for all subjects will be reported at the end of the study.

6.4. Biomarker(s)

As yet, no clear surrogate endpoints have been widely accepted that clearly define clinical outcomes for the multi-organ system manifestations of SLE. However autoantibodies have been shown to be important early markers of specific disease processes or severity in SLE [Hahn, 1998; Leslie, 2001; Ravirajan, 2001] and are associated with disease activity [Villarreal, 1997]. Therefore autoantibody levels will be included as endpoints.

Blood samples will be collected pre-dose at the visits specified in the Time and Events schedule (Table 2 and Table 3), to enable the following endpoints to be assessed:

- Percent change from baseline:
 - Total serum immunoglobulin (IgG and other isotypes: IgM and IgA)
 - Autoantibodies (anti-dsDNA) and complement (C3, C4)
- Percent change in absolute B cell subsets (CD20+, CD20+/27+ memory, CD20+/27- naïve, CD20+/69+ activated, CD20+/138+ plasmacytoid, CD19+/27BRIGHT/38BRIGHT SLE subset and CD20-/138+ plasma cells) at the Exit visit and 6 month Follow-up at selected sites.

All biomarker samples will be analysed centrally.

6.5. Pharmacokinetic Assessments

No PK sampling independent of immunogenicity testing, or liver chemistry stopping and follow-up criteria will be done. Immunogenicity samples will be tested for drug

levels using the belimumab PK assay to assist in the interpretation of the immunogenicity results.

7. DATA MANAGEMENT

For this study subject data will be entered into electronic case report forms (eCRFs), transmitted electronically to GSK or its partner company, HGS, and combined with data provided from other sources in a validated data system.

Management of clinical data will be performed in accordance with applicable GSK standards and data cleaning procedures to ensure the integrity of the data, e.g., removing errors and inconsistencies in the data. Adverse events and concomitant medications terms will be coded using MedDRA and an internal validated medication dictionary. eCRFs (including queries and audit trails) will be retained by GSK, and copies will be sent to the investigator to maintain as the investigator copy. In all cases, subject initials will not be collected or transmitted to GSK according to GSK policy.

Data from C1115 Day 168 will be entered into the eCRF for C1115 and programmatically merged with the BEL114333 datasets. Any data cleaning procedures performed on this C1115 data will be completed in the C1115 eCRF before the final data transfer into BEL114333.

8. DATA ANALYSIS AND STATISTICAL CONSIDERATIONS

There is no statistical sample size calculation. All analyses will be performed using descriptive statistics and will be exploratory in nature. The data base will be locked once all subjects have completed the Week 16 follow-up visit. Immunogenicity and B cell marker data collected at the 6-month post-treatment visit will be reported separately as an addendum to the clinical study report. Details of the analysis will be given in the Reporting and Analysis Plan (RAP).

8.1. Data Analysis Considerations

8.1.1. Primary Efficacy Analysis

The number and percent of subjects who respond at each scheduled visit when complete efficacy evaluations occur will be tabulated by treatment groups according to the treatment group that the subjects were assigned to during randomisation in BEL113750 study and the actual treatment they receive in the current study. The baseline will be defined as study Day 0 of BEL113750 study. Additionally, for the group of subjects who received placebo in BEL113750, a secondary analysis will be performed by defining the baseline as Day 0 of the current study the day placebo subjects in BEL113750 will have begun to receive belimumab treatment.

Subjects who previously received SC belimumab will be evaluated separately and this analysis will be described in the Reporting and Analysis Plan.

8.1.2. Analysis of Additional Efficacy and Biomarkers

For the primary analysis of the additional efficacy and biomarkers, the baseline will be defined as study Day 0 of BEL113750 Study. Additionally, for the group of subjects who received placebo in BEL113750 study, a secondary analysis will be performed by defining the baseline as the day placebo subjects in BEL113750 will have begun to receive belimumab treatment.

The major analysis of the additional efficacy and biomarkers will include the descriptive tabulation of secondary endpoints by treatment groups according to the treatment group that the subjects were assigned to during randomisation in BEL113750 study and the actual treatment they are assigned to in the current study.

Subjects who previously received SC belimumab will be evaluated separately and this analysis will be described in the Reporting and Analysis Plan.

8.1.3. Analysis of Safety Variables

AEs will be graded for severity by the investigator using Adverse Event Severity Grading Tables ([Appendix 6](#)) or the grades in Section 6.3.4, as appropriate. The frequency of AEs will be tabulated by MedDRA system organ class and preferred term and by treatment groups, according to the treatment group that the subjects were assigned to during randomisation in the BEL113750 or C1115 study. Additional analysis may be performed based on event rates adjusting for subject-years on study agent. The number of subjects with AEs and the incidence rate of AEs will be summarised in each 6-month time interval. AEs will also be summarised by MedDRA SOCs and preferred terms for those that are considered to be at least possibly related to study agent and those that are considered to be severe (Grade 3 and Grade 4). Discontinuations due to AEs will be summarised.

The frequency of laboratory abnormalities will be tabulated by treatment group. Laboratory values will be assessed for significant changes from baseline. Laboratory toxicity will be graded using Adverse Event Severity Grading Tables when possible. Shift tables will be used to determine if subjects move from normal to abnormal during the course of the study. Shifts of ≥ 2 grades and Grade 3 or Grade 4 laboratory abnormalities will be summarised.

Immunogenicity (anti-belimumab antibodies) will be summarized at baseline and during treatment and follow-up.

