2.2. Study Objective(s) and Endpoint(s)

Objectives	Endpoints	
Primary Objectives	Primary Endpoints	
Evaluate long-term safety and tolerability of belimumab in subjects with SLE in Japan and Korea	The endpoints below will be used to assess this study objective.	
	Adverse events (AEs)	
	 Frequency and percentage of subjects with events. Event rates adjusting for person-years on study agent. Laboratory Parameters Observed and Change from Baseline by visit. Laboratory reference shifts from baseline by visit. Laboratory toxicity worsening of at least two grades from baseline by study year Grade 3 or 4 laboratory abnormalities by visit and study year. 	
	Immunogenicity	
	Immunogenic response (anti-belimumab anti-bodies) by visit and study year.	
	Biomarkers	

[figure not shown]
Objectives	Endpoints
Coonday Objectives	 Percent change from baseline in immunoglobulins, auto-antibodies, and complement levels by visit. Immunoglobulin values below the lower limit of normal by visit and study year. Percent change from baseline in absolute B cell subsets.
Secondary Objectives	SRI and Other Secondary Endpoints
Evaluate the long-term efficacy of belimumab in subjects with SLE in Japan and Korea	SRI response rate at each scheduled visit when complete efficacy evaluations occur (e.g., Week 24 and Week 48 for each year). An SRI response is defined as
	 ≥4 point reduction from baseline in SELENA SLEDAI score, AND
	No worsening (increase of <0.30 points from baseline) in Physician's Global Assessment (PGA), AND
	 No new BILAG A organ domain score or 2 new BILAG B organ domain scores compared with baseline at the time of assessment.
	 Percent of subjects with ≥4 point reduction from baseline in SELENA SLEDAI score assessed every 24 weeks Percent of subjects with No Worsening in PGA compared
	to baseline (added to the RAP)
	Percent of subjects with No new BILAG A organ domain or 2 new BILAG B organ domain scores compared to baseline (added to the RAP)
	 Number of days of daily prednisone dose ≤ 7.5 mg/day
	and/or reduced by 50% from baseline over time.
	Time to first severe SLE Flare Index (SFI) flare assessed over time.
	Other Efficacy Endpoints
	Disease Activity
	Absolute change and percent change from baseline in SELENA SLEDAI (added to the RAP)
	Change in Systemic Lupus International Collaborating Clinics (SLICC)/ACR Damage Index assessed every 24 weeks.
	SLICC/ACR Damage Index Worsening from baseline (added to the RAP).

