7.4.1. Clinical Laboratory Evaluations

- Laboratory parameters which are continuous numeric values will be analyzed using summary statistics, and those with categorical results will be summarized using frequencies and percentages.
- Analyses will be performed based on the observed data. Only central laboratory data will be summarized.
- Refer to Appendix 5: Derived and Transformed Data for handling of laboratory values that are above or below the lower limit of quantification.
- Listings will be generated for all laboratory results, and additionally for Grade 3 or Grade 4 laboratory toxicity results.
- Baseline is defined as described in Section 11.4.2 and a list of laboratory parameters collected and definition of the toxicity grades provided in Appendix 9: Laboratory Parameters & Adverse Events Grading Tables.
 - Note: UREA is collected in BEL114333/BEL113750 and BUN is collected in BEL112341. "Urea (mmol/L) & BUN (mmol/L)" will be displayed as a single parameter in tabular summaries of laboratory parameters and a footnote added to highlight that different tests were performed in the different studies.
 - Note: Bilirubin direct data were not collected during the parent study for BEL112341 subjects; thus, because of missing data at baseline and postbaseline visits for the first 6 months of belimumab treatment (and data for the subsequent 12 months is limited to the placebo group), these subjects will be excluded from this summary.
- Toxicities will be reported as derived by the GSK EDU, as protocol toxicity grading was applied (or as assigned programmatically in the ADaM dataset creation, for lymphocytes, spot urine protein creatinine ratio and urine RBC). Note: toxicity data for partial thromboplastin time and prothrombin time will not be summarised because the data were only collected in the parent study. However, PT/PTT at baseline will be displayed in tabular summaries of laboratory parameters (see Section 7.4.2).

Additionally, for potassium, glucose, calcium and sodium, toxicities are bi-directional (i.e. high or low directions) and both will be summarised by name of the toxicity.

- Potassium: hypokalemia, hyperkalemia
- Glucose: hypoglycemia, hyperglycemia
- Calcium: hypocalcemia, hypercalcemia
- Sodium: hyponatremia, hypernatremia

For example, calcium will have two toxicity sections, one for hypocalcemia and one for hypercalcemia and mapped to their high or low as

- RESULT < (LLN+ULN)/2 = "Hypo" toxicity

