7.4.3. Worst laboratory toxicity grade post-baseline

• Toxicity grading for each analyte will be summarized. This reflects the worst grade for each analyte across all subjects and all assessments for each year interval and at any time post-baseline. The display will summarize the number (%) of subjects for each of the toxicity grades.

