7.4.4. Shift in Laboratory toxicity grade post-baseline

- Toxicity grade shifts from baseline of ≥ 2 grades for each analyte will be summarized for each year interval and at any time post-baseline. The display will summarize the number (%) of subjects with at least one ≥ 2 grade shift as well as the specific shift categories: Grade 0 to 2, Grade 0 to 3, Grade 0 to 4, Grade 1 to 3, Grade 1 to 4, and Grade 2 to 4.
- See Appendix 2: Assessment Windows for handling of the post-last dose 16 Week follow-up visit.

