7.4.5. Laboratory Reference Range Shifts

- Summaries will be presented by parent randomized treatment group, and total Safety population.
- Laboratory reference range shifts will be summarized only for laboratory tests without toxicity grades.
- A laboratory value that is outside of normal range will be considered abnormal (above or below).
- Shifts relative to the normal range will be summarized for each analyte, at each belimumab visit, as follows:
 - o 'n' represents the number (%) of subjects with a low, high or normal value at the specified visit.
 - o For subjects with a low value at the specified visit, the shift categories relative to baseline are shown as either remained low, or normal/high to low.
 - o For subjects with a high value at the specified visit, the shift categories relative to baseline are shown as either remained high, or normal/low to high.

 For subjects with a normal value at the specified visit, the shift categories relative to baseline are shown as either remained normal, or high to normal, or low to normal.

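### SAP 7.4.5 restricts reference-range shift tables to tests without toxicity grades, so a move from normal to high in a test graded only for low values is counted in no laboratory shift or toxicity table

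*Protocol*

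**What the plan says.** Protocol section 8.1.3, on laboratory safety: "Shift tables will be used to determine if subjects move from normal to abnormal during the course of the study". A separate sentence adds: "Shifts of ≥ 2 grades and Grade 3 or Grade 4 laboratory abnormalities will be summarised".

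SAP section 2.2 places this entry under the primary objective, without qualification: "Laboratory reference shifts from baseline by visit".

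SAP section 7.4.5 then says: "Laboratory reference range shifts will be summarized only for laboratory tests without toxicity grades". The same section treats any value outside the normal range, above or below, as abnormal.

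For graded tests the SAP offers by-visit descriptive statistics (section 7.4.2), a worst-grade table (section 7.4.3: "The display will summarize the number (%) of subjects for each of the toxicity grades") and a grade-shift table (section 7.4.4: "Toxicity grade shifts from baseline of ≥ 2 grades for each analyte will be summarized for each year interval and at any time post-baseline"). On direction, section 7.4.1 says: "for potassium, glucose, calcium and sodium, toxicities are bi-directional (i.e. high or low directions) and both will be summarised by name of the toxicity".

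SAP Table 1 has no row on laboratory shift tables.

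**The concern.** Dropping graded tests from the reference-range shifts would lose nothing if the grades covered the same ground. They do not. Where a test is graded only for low values, a newly high value has no grade, so the toxicity tables cannot show it, and section 7.4.5 keeps it out of the shift tables as well.

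Long-term safety is the primary objective and laboratory parameters are primary endpoints. At stake is a subject count that the protocol commits to. A reader of the study report who looks for the number of subjects moving from normal to high leukocytes, phosphate or magnesium would not find it, and SAP Table 1 would not tell them that it had been dropped.

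**Working it through.** There is no stated figure to reproduce. The check compares the tests marked as graded (SAP section 11.9.1), the direction of each grade (SAP section 11.9.2, Protocol Appendix 6) and the planned laboratory tables (SAP sections 7.4.2 to 7.4.5, Tables 2.56 to 2.80).

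**1. Direction of grading, legible starred tests**

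| Graded for | Tests | Count |
|---|---|---|
| Both directions | sodium, potassium, calcium, glucose | 4 |
| Low only | leukocytes, magnesium, phosphate, albumin, IgG | 5 |
| High only | AST, ALT, alkaline phosphatase, GGT, creatinine, total bilirubin, uric acid, urine protein, urine RBC, spot protein:creatinine ratio | 10 |

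4 + 5 + 10 = 19. The haematology differential in section 11.9.1 is not legible in the text available. The grade table grades haemoglobin, absolute neutrophils and platelets for low values only. If they too are starred, the low-only group is 5 + 3 = 8.

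**2. A low-only test going from normal to above the range**

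- Worst-grade table: counts subjects by grade. The value has none.
- Grade-shift table: covers 0 to 2, 0 to 3, 0 to 4, 1 to 3, 1 to 4 and 2 to 4. The subject stays at Grade 0.
- Reference-range shift tables 2.74 to 2.80: the test is excluded by section 7.4.5.
- By-visit tables: summary statistics only. Section 5.1 includes the maximum, so an extreme value shows there without a count.
- Listings 29 to 34: individual values.
- AE tables: only if the investigator judges the abnormality clinically significant (Protocol section 6.3.3).

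**3. Gaps in the graded direction**

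- Grade 0 to Grade 1 is not among the six shift categories, and the worst-grade table is not crossed with baseline.
- AST, ALT, GGT and alkaline phosphatase start Grade 1 at 1.25 x ULN. A value of 1.2 x ULN is above 1.0 x ULN, so abnormal under section 7.4.5, and below 1.25 x ULN, so ungraded.
- This second gap is not general. Creatinine and total bilirubin are graded from just above 1.0 x ULN. IgG Grade 1 starts at 700 mg/dL = 7.00 g/L, which is above the SAP's lower limit of 6.94 g/L.

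**4. Tests covered elsewhere**

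- Spot protein:creatinine ratio: shifts across 0.5 mg/mg by visit and at any time on treatment (SAP section 8.2.10, Table 3.26).
- Low IgG: counted by visit and by year interval (SAP section 9.1.2, Tables 5.3 to 5.5). High IgG after baseline is not.

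**The case against.** The strongest reply is that the protocol is less specific than it looks. Section 8 leaves analysis details to the Reporting and Analysis Plan, and section 8.1.3 says that toxicity will be graded when possible before it mentions shift tables. On that reading, grade shifts serve the graded tests and range shifts serve the rest, and every graded test keeps a shift table that includes Grade 0 to Grades 2, 3 and 4. This is a fair account of the graded direction from Grade 2 upward. It cannot cover a direction that has no grade, and the protocol lists grade shifts in a sentence of their own, which suggests an addition rather than a substitute.

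A second reply is that the clinical signals are measured directly. Creatinine is graded from just above ULN; urea and estimated creatinine clearance carry no star, so they keep range shifts; renal flare and proteinuria are analysed; infections and steroid dose have their own tables. This stands, and it limits the harm.

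A third is that SAP section 11.5.1 mentions High and Low categories over any post-baseline visit, and tables of potential clinical importance. Appendix 12 lists no such laboratory table, so this does not close the gap.

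Stronger readings are tempting, and the documents do not support them:

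- A reader might infer that all 19 graded tests lose their shift information. The protein:creatinine ratio and low IgG are tabulated elsewhere. Ten of the 15 one-way tests are graded high only, and for several of those a low value says little.
- A reader might infer that these subjects are in no table at all. Clinically significant abnormalities enter the AE tables.
- A reader might take a particular leukocyte or platelet value as abnormal but ungraded. The documents give no reference limits for these tests, so only the general statement, any value above ULN, is safe.
- A reader might infer that no neutrophil excess can be counted. Protocol Appendix 5 lists segmented and band neutrophils separately from the absolute count, and only the absolute count has a grade. The others might keep range shifts.

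**Conclusion.** The point holds in a narrow form and is minor. Two unrestricted statements, one in the protocol and one in the SAP's own endpoint list, conflict with an undeclared restriction in SAP section 7.4.5. The practical loss is the normal-to-high count for five legible low-only tests, or eight if haemoglobin, absolute neutrophils and platelets are starred as the grade table implies. The lesser losses are Grade 0 to Grade 1 shifts, and liver enzymes between 1.0 and 1.25 x ULN.

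This assumes that a value with no grade is handled as Grade 0, and that section 7.4.5 will be applied as written. The study tests no hypothesis and the raw values are listed, so no inference is affected. What is missing is a descriptive safety count.

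**What to change.** Amend SAP section 7.4.5 so that Tables 2.74 to 2.80 also include each low-only graded test for shifts from baseline to above the reference range. Optionally, add normal-to-abnormal shifts for AST, ALT, GGT and alkaline phosphatase. Record whatever restriction remains in SAP Table 1, with the reason.

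For IgG the upper limit has to be stated: SAP section 11.5.5 gives only the lower limit and merges normal with high.

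The cost is SAP wording and somewhat longer tables, about eight tests, or twelve with the four liver enzymes (8 + 4). The shell (SAFE_T20) already exists and no new data are needed. Running every graded test in full is not needed, as it would largely repeat the grade tables.
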